8.1.8 Adverse Event Assessment

An adverse event assessment will be completed by the investigator at the end of the baseline visit.

8.2 Chronic Period

8.2.1 Chronic Period Instructions

Prior to starting the chronic period, the “Omnidirectional” program will be deleted from the M90 processor and subjects will exclusively use AutoSense on the investigational M90 processor with a T-mic (EO cohort) or an acoustic earhook with a dome (ARH cohort) for 14-21 days during their everyday activities. Slight adjustments may be made to the programming, as needed.

Once the subject has returned the processor to the study site, the Investigator will connect the processor to the Target CI fitting software and create a session to document the chronic use period.

8.2.2 Follow-Up Self-Assessment Questionnaire

Subjects will complete a custom self-assessment questionnaire on paper or through the EDC system 14 to 21 days after the baseline visit. If completed on paper, the questionnaire will be returned together with the investigational device.

8.2.3 Adverse Event Assessment:

An adverse event assessment is completed by the investigator at the end of the chronic period.

8.2.4 Device Return

Subjects will be provided a FEDEX envelope and airbill at the baseline visit and will return the investigational M90 processor after 14 to 21 days of chronic use.

8.3 Summary of Visit Activities

Procedure	Baseline Visit		Chronic Period
	EO Cohort	ARH Cohort	
Informed Consent	✓	✓	
Demographics & Audiological History	✓	✓	
Audiometric Thresholds	✓	✓	
Confirmation of Eligibility	✓	✓	
Custom Self-Assessment Questionnaire	✓	✓	✓
AutoSound on the Q90 Processor	AzBio in Quiet	✓	✓
	AzBio in Noise	✓	✓
AutoSense on the M90 Processor	AzBio in Quiet	✓	✓
	AzBio in Noise	✓	✓
“Omnidirectional” program on the M90 Processor	AzBio in Noise	✓	✓
Adverse Event Assessment	✓	✓	✓
Device Accountability	✓	✓	✓

9.0 Statistical Methods and Sample Size

9.1 General Considerations

The two cohorts to be separately evaluated are the Electric Only (EO) cohort (n=12 pairs) and the Aidable Residual Hearing (ARH) cohort (n=12 pairs). The sample size includes an allowance for dropouts.

The following data will be collected and evaluated as part of this study:

- Speech recognition in quiet (primary efficacy endpoint) for the investigational AutoSense on a M90 processor vs. AutoSound on the Q90 processor (control).
- Speech recognition in noise (secondary efficacy endpoint) with AutoSense on a M90 processor vs. AutoSound on a Q90 processor.

Evaluation of AutoSense OS on a Naída CI M90 Sound Processor Programmed with Target CI Fitting Software in Adult Users of the HiResolution Bionic Ear System

- Increased speech recognition in noise (secondary efficacy endpoint) with a M90 sound processor when comparing the manual “Omnidirectional” program to AutoSense.
- Subjective feedback (subjective endpoint) about the use of AutoSense on a M90 processor in everyday listening situations.

Descriptive statistics will consist of counts, means, and standard deviations for quantitative variables (primary and secondary outcome measures) and frequency and percent relative frequency for categorical variables.

9.1.1 Data Analyses

9.1.1.1 Efficacy Endpoints

The primary efficacy endpoint is speech recognition on AzBio in quiet mode for AutoSense on the M90 processor vs AutoSound on the Q90 processor. Non-inferiority analyses will be based on paired t-tests looking at the differences in scores calculated using the Experimental results minus the Control scores at the baseline visit. A one-sided hypothesis test will be used with 0.05α for the primary efficacy evaluation evaluating the following hypothesis:

$$H_0: \mu_{\Delta} \leq -0.10 \text{ versus } H_1: \mu_{\Delta} > -0.10$$

where μ_{Δ} is the mean of the difference (AutoSense on M90 – AutoSound on Q90) on the AzBio sentence test in quiet. A non-inferiority bound of 0.10 (10%) was selected for the AzBio test based on procedures used in previous studies [REDACTED]

[REDACTED] Statistically significant test results that reject the null hypotheses, indicating that the means of the paired differences are greater than -0.1 (-10%) for AzBio in quiet mode, which will support that the Investigational condition is non-inferior to the Control condition.

The primary and secondary efficacy endpoints will be first considered for non-inferiority and then for superiority. The superiority tests are penalty-free since the alternative hypothesis for superiority is nested within the alternative hypothesis for non-inferiority. The superiority test will use one-sided $p=0.025$.

Additional analyses will be conducted to assess any differences based on age of onset or duration of sensorineural hearing loss (SNHL). An analysis of variance (ANOVA) will be used to model the paired differences (Investigational – Control) of AzBio sentences in quiet age of onset and duration of SNHL as the covariate. The analysis will be repeated for AzBio sentences in noise as well as for sentence recognition. The results will also be presented by age of onset and duration of SNHL.

Because the study includes a single visit followed by a chronic period with a subjective questionnaire, the possibility exists that some study participants will not complete the entire test protocol. Given the study design, no data will be imputed but efficacy analysis for other primary and secondary effectiveness endpoints will be repeated for the subset with missing data. In addition, to accommodate potential losses, additional subjects will be enrolled beyond the required sample size per cohort. Efficacy data will not be combined across cohorts.

9.1.1.2 *Type 1 Error Control*

The study will have one primary and two secondary efficacy endpoints per cohort. The Type 1 error needs to be preserved for the two cohorts and three primary and secondary efficacy endpoints.

To address the two independent cohorts, the usual testing for one cohort would rely on one-sided $\alpha=0.05$ but to independently test each cohort, the α will be set to 0.025 to allow testing to be cohort specific. Then results could be separately tested per cohort which would allow significance claims to be made for only one cohort. Then cohort-specific testing will be justified.

For primary and secondary efficacy endpoint testing per cohort, Type I error will be preserved using hierarchical testing where the primary efficacy endpoint will be tested first and then the two secondary efficacy endpoints will be tested next in the pre-specified order (see Section 6.2.1). Cohort-specific claims will be supported for the ordered testing of primary and secondary efficacy endpoints until statistical significance was no longer reached. Thus, to claim statistical significance for all three endpoints, each would need to reach non-inferiority; the subsequent testing for superiority would be penalty-free so the failure to reach superiority would not stop subsequent endpoints from being declared significant based on non-inferiority.

9.1.1.3 *Analyses of Individual Results*

A critical difference score will be used to determine whether individual subjects demonstrate a significant decrease in performance between the Experimental (AutoSense on M90) and Control (AutoSound on Q90) conditions. Specifically, the criterion value for the critical difference score will be based upon the test-retest variance on the AzBio test. Gifford (2008) provided a set of data on 35 listeners for the AzBio sentences, wherein two lists of sentences were presented one after the other to cochlear implant recipients. Based on those data, the expected variability between lists has a standard deviation σ of 3.8%. The critical difference score can be computed based on the assumption that (1) the difference scores have a normal distribution, and (2) the difference scores are deemed significant if, under the null hypothesis, the probability of the difference score exceeding the critical score is 1%. Under these assumptions, the critical improvement (or decrement) score CS is equal to:

$$CS = \sigma * b$$

In the above equation, $b = 2.33$, the percentile of the normal curve corresponding to the desired values of $\alpha = 0.01$, one-tailed test. Using Gifford's σ value, the critical difference score for AzBio sentences is 8.9%.

The number and percentage of subjects exceeding, within, and below the critical difference (Investigational - Control) score will be tabulated. The shift from the baseline assessments will be summarized for both the Experimental and Control results indicating *improved*, the *same*, or *deteriorated*. Further the difference between the two strategies will be evaluated and classified as better for the Experimental strategy, the same for both strategies, or better for the Control strategy. A two-sided exact binomial test will be used to evaluate the null hypothesis that the distribution of subjects showing a performance difference (Investigational is better or Control is better) is distributed equally. This analysis will

Evaluation of AutoSense OS on a Naída CI M90 Sound Processor Programmed with Target CI Fitting Software in Adult Users of the HiResolution Bionic Ear System

provide an additional indication of the efficacy of AutoSense on the M90 processor relative to AutoSound on the Q90 processor based upon individual data.

9.1.1.4 *Safety Endpoint*

The primary safety objective is to evaluate whether there are adverse events related to use of AutoSense OS or the M90 processor that impact device safety.

9.1.1.5 *Supporting Data*

Acceptability questionnaire data will be analyzed descriptively using frequency and percent relative frequency for categorical variables.

9.1.2 *Sample Size Justification*

A total sample size of 12 subjects per cohort is planned for this study based upon efficacy and safety considerations. Previous cohort-specific data were used to estimate the standard deviations (SD) for the paired M90-Q90 differences. The minimum number of subjects required for the study was calculated based upon the primary efficacy outcome measures. The primary efficacy objective is to demonstrate non-inferiority of AutoSense on the M90 processor compared to AutoSound on the Q90 processor for the AzBio sentence test in quiet mode based on a paired t-test. The primary efficacy analyses will test the null hypothesis that the mean of the paired differences (μ_{Δ}) in AzBio sentence scores in quiet mode (AutoSense on M90 – AutoSound on Q90) are less than or equal to -10 percentage points, where:

$$H_0: \mu_{\Delta} \leq -10\% \text{ versus } H_1: \mu_{\Delta} > -10\%$$

Demonstrating that the mean difference, μ_{Δ} , is greater than -10 percentage points for all three test conditions will be considered to have shown that M90 is non-inferior to Q90. For both cohorts, previous data supported 6.24% SD for the primary efficacy endpoint (labelled 1 below) and 6.61% SD for the first secondary efficacy endpoint (labelled 2 below). As shown in Table X below, there is >90% power per cohort and per endpoint (power columns) to rule out a -10% null hypothesis supporting non-inferiority (N-I) for a one-sided 2.5% test with statistical significance (one-sided $p=0.025$) achieved when <-4.98% and <-4.64% paired mean disadvantages are observed while superiority (reach one-sided $p=0.025$) would be achieved if >5.02% and >5.32% paired mean advantages are observed. The calculations below are based on 8 complete pairs per cohort; a total of 12 pairs will be enrolled in order to accommodate up to four losses per cohort.

Table 4: Paired t-tests to reject the null hypotheses for non-inferiority and superiority

	Power		Reach N-I		Reach Sup	
	1	2	1	2	1	2
Test significance level, α	0.025	0.025	0.025	0.025	0.025	0.025
Null hypothesis mean difference, μ_0	0%	0%	-4.98%	-4.64%	0%	0%
Alternative mean difference, μ_A	-10%	-10%	-10%	-10%	-5.02%	-5.32%
Paired SD, σ	6.24%	6.61%	6.24%	6.61%	6.24%	6.61%
Effect size, $\delta = \mu_A - \mu_0 / \sigma$	1.603	1.513	0.805	0.810	0.804	0.805
Power (%)	94	90	NA	NA	NA	NA
N pairs	8	8	8	8	8	8

These calculations are based on the T-distribution non-centrality factor as follows:

$$T_{n,NCF} = \frac{\sqrt{n}(\mu_A - \mu_0)}{\sigma}$$

observed based on the non-centrality factor:

$$Power = T_{n-1}(T_{n-1}^{-1}(0.95), n - 1, \delta = T_{n,NCF})$$

The sample size (16) can provide sufficient data for determining the safety and reliability of the new strategy. Based on a sample size of 24, the upper bound of the exact event rate was calculated in order to provide complication rates. If no events are observed in 16 subjects, then 15.3% is the upper bound for a one-sided 95% confidence interval on this event rate. This bound provides assurance that events not observed will appear in less than 17.1% of subjects.

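### Section 9.1.1.1 sets the primary test at one-sided 0.05, but Section 9.1.1.2 and Table 4 require 0.025 per cohort; at 0.05 the chance of a false non-inferiority claim across the two cohorts reaches 9.75%, not 5%

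*Combined protocol and SAP*

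**What the plan says.** Section 9.1.1.1 gives the primary hypothesis (mean paired difference above −10 points) and its level: "A one-sided hypothesis test will be used with 0.05α for the primary efficacy evaluation evaluating the following hypothesis". It does not call 0.05 an overall level and does not point to the section on Type 1 error. It gives 0.025 only to the superiority test that follows non-inferiority. It also says: "Efficacy data will not be combined across cohorts".

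Section 9.1.1.2 sets the aim: "The Type 1 error needs to be preserved for the two cohorts and three primary and secondary efficacy endpoints". It describes one-sided 0.05 as the usual level for a single cohort, and then says: "to independently test each cohort, the α will be set to 0.025 to allow testing to be cohort specific". The reason given is a structure "which would allow significance claims to be made for only one cohort".

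Section 9.1.2 describes its calculations as "for a one-sided 2.5% test with statistical significance", and every column of Table 4 shows 0.025. The power formula printed below the table takes the 0.95 quantile of the t distribution, which corresponds to one-sided 0.05.

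**The concern.** Two places in the plan (the primary hypothesis and the power formula) point to 0.05, and two (Section 9.1.1.2 and Table 4) point to 0.025. No text says which takes precedence. Read alone, 9.1.1.1 looks deliberate: non-inferiority at 0.05, then superiority at 0.025.

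The primary result in each cohort therefore depends on which paragraph the analyst follows. The primary test is also the gate for the two secondary endpoints in that cohort, so the choice decides whether they are tested at all. If the level is settled only after the data are seen, either choice can look driven by the result.

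**Working it through.** **Inputs.** Level 0.05 (9.1.1.1) or 0.025 (9.1.1.2 and Table 4), one-sided. Margin 10 points (9.1.1.1). Paired SD 6.24 points for the primary endpoint and 6.61 for the first secondary; 8 complete pairs per cohort in the calculation and 12 enrolled (9.1.2). Section 9.1.1.2 treats the cohorts as independent, and efficacy data are not pooled.

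**1. The plan's own level.** Splitting the usual 0.05 over two cohorts gives 0.05 / 2 = 0.025, which reproduces Section 9.1.1.2.

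**2. Error across cohorts.** For two independent tests at level α, with both true means exactly at the −10 point margin, the chance of at least one false claim is 1 − (1 − α)².

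| Level per cohort | Formula | Result | Simulated, n = 8 | Simulated, n = 12 |
|---|---|---|---|---|
| 0.05 | 1 − 0.95² | 9.75% | 9.8% | 9.7% |
| 0.025 | 1 − 0.975² | 4.94% | 4.9% | 5.0% |

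The simulations applied the paired t-test to normal differences with mean −10 and SD 6.24.

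**3. Where the two rules disagree.** At the planned SD, non-inferiority is reached when the observed mean exceeds −10 + t(1−α, n−1) × 6.24 / √n.

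- n = 8, standard error 6.24 / √8 = 2.206. At 0.05: −10 + 1.895 × 2.206 = −5.82. At 0.025: −10 + 2.365 × 2.206 = −4.78.
- n = 12, standard error 6.24 / √12 = 1.801. At 0.05: −10 + 1.796 × 1.801 = −6.77. At 0.025: −10 + 2.201 × 1.801 = −6.04.

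A mean inside the band passes at 0.05 and fails at 0.025. The band is about 1.0 point wide at n = 8 and 0.7 at n = 12.

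**4. Power.** Power is 1 minus the noncentral-t distribution function at the critical value, with n − 1 degrees of freedom and noncentrality √n × 10 / SD, for a true difference of zero. With n = 8 the noncentrality is 4.53 (SD 6.24) or 4.28 (SD 6.61).

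| One-sided level, n = 8 | Primary (SD 6.24) | First secondary (SD 6.61) |
|---|---|---|
| 0.05 | 99.2% | 98.5% |
| 0.025 | 97.1% | 95.4% |
| Table 4 as printed | 94% | 90% |

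Table 4's power figures reproduce at neither level with 8 pairs, so they cannot show which level was used. That is a separate defect.

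**5. When the choice matters.** For the primary endpoint the two rules pass 99.2% and 97.1% of cohorts at n = 8 if the true difference is zero. If it were −5 points (an illustrative value, not from the plan), they would pass about 65% and 50% at n = 8, and about 83% and 72% at n = 12.

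**The case against.** The strongest reply is that the plan already resolves the matter. Section 9.1.1.2 is the section on Type 1 error; it names both levels, explains why it moves from 0.05 to 0.025, and is followed by Table 4. Table 4's primary cut-off of −4.98 lies near the 0.025 threshold (−4.78) and far from the 0.05 one (−5.82). On this reading the 0.05 in 9.1.1.1 is the single-cohort level left uncorrected, and the 0.95 in the formula is an editorial slip that decides no test. This is good evidence of intent and shows which way to correct the text. It does not remove the conflict: 9.1.1.1 is the operative statement of the primary test, and an analyst following it would be following the plan.

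The reply adds that 9.75% is a worst case, and that the plan never states an overall 5%. Both are true. The maximum over the null hypothesis is nevertheless what Type 1 error control must bound, and 5% follows from halving the level the plan calls usual.

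Finally, under the planned assumptions the two rules rarely differ: in about 2.1% of cohorts at n = 8 and 0.1% at n = 12 (99.98% against 99.89% power). That also stands, but it assumes no true difference. The level matters when the true difference is nearer the margin.

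**Conclusion.** The concern holds, and the plan is wrong as written. The decision threshold for the primary endpoint is stated two ways. Followed as 9.1.1.1 reads, the trial could make at least one false primary non-inferiority claim with probability up to 9.75%, about twice the 4.94% that the split in 9.1.1.2 delivers. These figures assume independent cohorts and both true means at the margin; the bands of observed means that change the conclusion also assume an SD of 6.24 points. This must be fixed before data are seen, because it governs the primary result and entry to the secondary tests.

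**What to change.** In Section 9.1.1.1, replace the 0.05 level with one-sided 0.025 within each cohort (overall one-sided 0.05 across the two cohorts), state that it applies to every non-inferiority test, and refer to Section 9.1.1.2. In the Section 9.1.2 formula, replace 0.95 with 0.975 and write power as 1 minus the noncentral-t distribution function.

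The cost is wording only. At one-sided 0.025 with 8 pairs, power is 97.1% for the primary endpoint and 95.4% for the first secondary, both above the plan's 90%, so the sample size need not change.

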Evaluation of AutoSense OS on a Naída CI M90 Sound Processor Programmed with Target CI Fitting Software in Adult Users of the HiResolution Bionic Ear System

	ear
Exclusion Criteria All Cohorts	
 • Unrealistic expectations regarding potential benefits, risks and limitations of the investigational device as determined by the investigator • Unwillingness or physical / cognitive inability of subject to comply with all investigational requirements as determined by the investigator
Primary Efficacy Objective	The primary efficacy objective is to demonstrate that speech recognition in quiet with AutoSense on a M90 processor is no worse than speech recognition in quiet with currently approved software on a Q90 processor.
Secondary Efficacy Objective(s)	
The secondary efficacy objectives are
 
 • To demonstrate that speech recognition in noise with AutoSense on a M90 processor is no worse than speech recognition in noise with currently approved software on a Q90 processor. • To demonstrate increased speech recognition in noise with the M90 sound processor when comparing “Omnidirectional” program to AutoSense
Safety Objective	The primary safety objective is to evaluate whether there are adverse events related to the use of AutoSense on a M90 processor that impact device safety.
Primary Efficacy Endpoint	AzBio sentence scores in quiet at Baseline with AutoSense on a M90 processor as compared to AzBio sentence scores in quiet at Baseline with currently approved software on a Q90 processor
Secondary Efficacy Endpoint(s)	
 • AzBio sentence scores in noise at Baseline with AutoSense on a M90 processor as compared to AzBio sentence scores in noise at Baseline with currently approved software on a Q90 processor. • AzBio sentence scores in noise at Baseline with AutoSense on a M90 processor as compared to AzBio sentence scores in noise at Baseline with a manual “Omnidirectional” program on a M90 processor.
Safety Endpoint	Absence of unanticipated adverse device effects related to use of AutoSense on a M90 processor
Supporting Data	Analysis of non-standardized subject questionnaire after two weeks of use of AutoSense OS and a M90 processor in everyday listening situations.
Study Monitoring	Advanced Bionics, LLC [name] [REDACTED]

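### The AutoSense-versus-Omnidirectional endpoint aims to show an increase, but the claims rule lets it be declared significant on non-inferiority alone

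*Combined protocol and SAP*

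**What the plan says.** The Synopsis gives two secondary objectives of different kinds. The first is that AutoSense on the M90 is no worse in noise than the Q90. The second is directional: "To demonstrate increased speech recognition in noise with the M90 sound processor when comparing" the Omnidirectional program with AutoSense. Section 9.1 describes the same endpoint as "Increased speech recognition in noise (secondary efficacy endpoint) with a M90 sound processor when comparing the manual" Omnidirectional program with AutoSense. Section 6.2.1 lists it last, so it is the third and final test in each cohort's hierarchy (endpoint 3 below).

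The testing rules do not keep that distinction:

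- Section 9.1.1.1: "The primary and secondary efficacy endpoints will be first considered for non-inferiority and then for superiority", with superiority tested at one-sided 0.025. On the margin: "A non-inferiority bound of 0.10 (10%) was selected for the AzBio test based on procedures used in previous studies". The hypotheses are written out only for AzBio in quiet.
- Section 9.1.1.2, on claims: "Cohort-specific claims will be supported for the ordered testing of primary and secondary efficacy endpoints until statistical significance was no longer reached". It continues: "Thus, to claim statistical significance for all three endpoints, each would need to reach non-inferiority". It adds that "the failure to reach superiority would not stop subsequent endpoints from being declared significant based on non-inferiority".
- Section 9.1.2: a mean difference that "is greater than -10 percentage points for all three test conditions will be considered to have shown that M90 is non-inferior to Q90".

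Section 9.1.2 gives SDs and power for the primary endpoint and the first secondary endpoint only. It gives no SD, expected gain or power for endpoint 3.

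**The concern.** Endpoint 3 has a superiority objective and a non-inferiority success rule. The superiority test it needs is planned, but nothing says that endpoint 3 succeeds only if that test is passed. Followed as written, Section 9.1.1.2 allows a statement that all three endpoints reached statistical significance when the third has shown only that AutoSense is not more than 10 points worse than Omnidirectional. Because Section 9.1 labels the endpoint as increased recognition, such a statement is easily read as evidence of benefit.

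This matters because endpoint 3 is the only formal comparison of AutoSense with another program on the same processor. The two M90-versus-Q90 comparisons change processor and software together.

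**Working it through.** **The text, side by side.** The objective (Synopsis, Section 9.1) requires a mean difference, AutoSense minus Omnidirectional, above 0. The claims rule (Section 9.1.1.2) requires non-inferiority, that is, a mean difference above -10 points if the stated margin applies. No section exempts endpoint 3 from that rule. The Section 9.1.2 sentence adds little: it concludes that the M90 is non-inferior to the Q90, yet endpoint 3 has no Q90 arm, and the SDs and Table 4 beside it cover endpoints 1 and 2. It may be a wording slip, and the finding does not depend on it.

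**The plan's own power figures.** Section 9.1.2 states 94% and 90% for endpoints 1 and 2 (8 pairs, one-sided 0.025, margin 10, SDs 6.24% and 6.61%). The noncentral t with those inputs gives 97.1% and 95.4%, so the stated figures are not reproduced and are conservative. One-sided 0.0125 gives 92.3% and 89.0%; 7 pairs gives 93.9% and 91.2%. This mismatch is a separate matter.

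**Illustration for endpoint 3.** Inputs:

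- n = 8 complete pairs or 12 enrolled pairs per cohort (Section 9.1.2).
- One-sided alpha 0.025 per cohort (Section 9.1.1.2), so critical t is 2.3646 (7 df) or 2.2010 (11 df).
- Margin 10 points (Section 9.1.1.1), assumed to apply to endpoint 3.
- SD 6.61%, borrowed from the other noise endpoint. This is an assumption; 15% is used as a wide alternative.

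Formulas, taking the observed SD as the assumed SD for the thresholds:

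- Superiority threshold = t × SD/√n. For n = 8: 2.3646 × 6.61/√8 = 5.53. For n = 12: 2.2010 × 6.61/√12 = 4.20.
- Non-inferiority threshold = -10 + t × SD/√n, which is -4.47 or -5.80.
- Chance of passing non-inferiority at zero true difference = P(T' > t), where T' is noncentral t with n - 1 df and noncentrality √n × 10/SD. For SD 6.61 the noncentrality is 4.28 (n = 8) or 5.24 (n = 12).
- Passing superiority implies passing non-inferiority, so at zero true difference the two rules disagree with probability (pass rate - 0.025).

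| Assumed SD | Pairs | Non-inferiority if mean above | Superiority if mean above | Non-inferiority pass rate, true difference 0 | Rules disagree |
|---|---|---|---|---|---|
| 6.61% | 8 | -4.47 | +5.53 | 95.4% | 92.9% |
| 6.61% | 12 | -5.80 | +4.20 | 99.7% | 97.2% |
| 15% | 8 | +2.54 | +12.54 | 37% | 35% |
| 15% | 12 | -0.47 | +9.53 | 56% | 53% |

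A simulation of 400,000 trials gave disagreement of 93.0% and 97.3% (SD 6.61%) and 34.7% and 53.2% (SD 15%).

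**Other true differences, SD 6.61%, 8 and 12 pairs.**

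- AutoSense truly 5 points worse: non-inferiority still passes 45.5% and 66.6% of the time.
- True gain of 5 points: superiority passes about 45% and 67%, and the rules disagree in about 55% and 33%.
- True gain of 10 points: the rules disagree in 4.6% and 0.3%. At SD 15% this becomes 53% and 43%.

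The pass rates at zero difference are the power of the non-inferiority test, not its Type 1 error. They describe endpoint 3's test alone, before the gate of the two earlier tests.

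**The case against.** The strongest reply is that the right test already exists. Section 9.1.1.1 gives endpoint 3 a superiority test, the Synopsis keeps the two kinds of objective apart, and Section 9.1.1.2 labels declarations short of superiority as resting on non-inferiority. On this reading, the sentence about all three endpoints is a gatekeeping rule that states a necessary condition for testing down the hierarchy. It does not define when the objective of an increase is met, and only a cross-reference is missing. A reader with the confidence interval could see for themselves whether an increase was shown.

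Much of this is fair. A superiority test is planned, the label exists, and no section says that non-inferiority demonstrates an increase. But Section 9.1.1.2 is the only place that says which claims are supported. It covers endpoint 3 and sets the bar at non-inferiority. Planning a test does not make it the success criterion.

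It is also fair that the size of the disagreement rests on inputs the plan does not give. It runs from near 0 to 97% depending on the SD, the number of pairs and the true gain. The figures are therefore illustrative, and the conflict in the text does not rest on them.

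**Conclusion.** The concern holds. The success rule for endpoint 3 does not match its objective, and the endpoint can be declared significant with no gain. Under the borrowed 6.61% SD and 10-point margin, that declaration could come with an observed mean as low as about -4.5 points (8 pairs) or -5.8 points (12 pairs), and with no true gain it would be the usual result of that test. At an SD of 15% the gap is smaller but still large.

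The consequence is limited to one secondary claim per cohort. Endpoint 3 is tested last, so the primary endpoint, the first secondary endpoint and the alpha allocation are unaffected. It should be fixed, because a stated rule contradicts a stated objective and the repair is cheap if made before results are known.

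**What to change.** Keep the sequence of non-inferiority followed by superiority, and add to Sections 9.1.1.1 and 9.1.1.2:

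> Endpoint 3 (AutoSense minus Omnidirectional, M90, noise) is tested last in the hierarchy. Its success, and any claim of increased speech recognition, requires the superiority test (H0: mean difference ≤ 0, one-sided 0.025 per cohort). A non-inferiority result for endpoint 3 may be reported only as such, naming the margin used.

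In Section 9.1.2, limit the -10 point criterion to the two M90-versus-Q90 comparisons.

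This changes wording only. Data collection, alpha, sample size and the other two endpoints stay as they are. The cost is that endpoint 3 becomes harder to win: at the assumed SD of 6.61%, power for a true 5-point gain is about 45% with 8 pairs or 67% with 12. The added wording does not supply the missing SD, expected gain or power for endpoint 3. The sponsor should accept the endpoint on that footing or state its assumptions.

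### Superiority tests outside the hierarchy each get the full 0.025, so the chance of a false claim can reach about 7% per cohort against an intended 2.5%

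*Combined protocol and SAP*

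**What the plan says.** Section 9.1.1.2 states the aim: "The Type 1 error needs to be preserved for the two cohorts and three primary and secondary efficacy endpoints". For the two cohorts, "the α will be set to 0.025 to allow testing to be cohort specific". Within a cohort, the primary endpoint (AzBio in quiet, M90 against Q90) is tested first, then the two secondary endpoints in noise (M90 against Q90; AutoSense against Omnidirectional), until significance is no longer reached.

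The step from one endpoint to the next depends on non-inferiority only. On superiority the section says: "the subsequent testing for superiority would be penalty-free so the failure to reach superiority would not stop subsequent endpoints from being declared significant", and the sentence ends by tying that declaration to non-inferiority.

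Section 9.1.1.1 says that primary and secondary endpoints are each considered for non-inferiority and then for superiority, the latter at one-sided 0.025. Its reason is: "The superiority tests are penalty-free since the alternative hypothesis for superiority is nested within the alternative hypothesis for non-inferiority". Section 9.1.2 asks that the mean difference "is greater than -10 percentage points for all three test conditions", so the third endpoint carries a non-inferiority test too. Table 4 gives observed advantages at which superiority would be reached on endpoints 1 and 2 at 0.025. No section orders the superiority tests across endpoints, divides alpha among them, or calls them exploratory.

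**The concern.** The nesting argument is correct for one endpoint. There, superiority can be true only if non-inferiority is true, so testing one after the other at the same level costs nothing. It does not extend to superiority on endpoint 1 set beside the tests on endpoints 2 and 3. A fixed sequence controls the family error only when every confirmatory test is a step in it and a failure stops what follows. Here a superiority test hangs off each endpoint at full alpha, and its failure stops nothing.

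At stake is the error statement attached to a superiority claim, above all one over the Q90. Such a claim would be reported as part of a family controlled at 0.025 per cohort when that family is not controlled at that level.

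**Working it through.** **Inputs.** One-sided alpha 0.025 (9.1.1.2, 9.1.2). Margin -10 points on all three endpoints (9.1.2). Paired SD 6.24 for endpoint 1 and 6.61 for endpoint 2 (9.1.2). Pairs per cohort: 8 complete, 12 enrolled (9.1.2). Assumed, because the documents do not give them: SD 6.61 for endpoint 3, and correlations between the endpoints' paired differences of 0, 0.5 or 0.8.

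**Step 1: the plan's own figure.** For the non-inferiority chain alone, the first true null in the order must be rejected at 0.025 before any false claim can occur. With all true differences at -10, simulation gives 2.52% (n=8) and 2.55% (n=12). The 0.025 is reproduced for this chain.

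**Step 2: add the superiority tests.** Take all true differences as 0 and endpoints as independent. Let a = 0.025, and let p1 and p2 be the chances of reaching non-inferiority on endpoints 1 and 2. Superiority on an endpoint implies non-inferiority on it, so

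P(at least one false claim) = a + (p1 - a) × [a + (p2 - a) × a].

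The noncentral t gives p1 = 0.9709 and p2 = 0.9539 at n=8, and 0.9989 and 0.9973 at n=12.

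- n=8: 0.025 + 0.9459 × [0.025 + 0.9289 × 0.025] = 7.06%.
- n=12: 0.025 + 0.9739 × [0.025 + 0.9723 × 0.025] = 7.30%.
- Ceiling for independent tests: 1 - 0.975³ = 7.31%.
- Both cohorts: 1 - (1 - 0.0706)² = 13.6% and 1 - (1 - 0.0730)² = 14.1%.

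Table 4 prints powers of 94% and 90%, which the noncentral t does not reproduce at n=8. With the printed values the result is 0.025 + 0.915 × [0.025 + 0.875 × 0.025] = 6.8%, so the conclusion does not depend on that mismatch.

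**Step 3: a true gain over Omnidirectional, parity with the Q90.** Superiority on endpoint 3 is then no longer a false claim:

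P = a + (p1 - a) × a = 0.025 + 0.9459 × 0.025 = 4.86% (n=8), and 0.025 + 0.9739 × 0.025 = 4.93% (n=12).

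**Step 4: correlated endpoints.** Simulated paired t-tests under the written rule, with at least 200,000 trials per setting (standard error at 2.5% about 0.035 points). Ranges cover n=8 and n=12; the independent column is the exact calculation where one is shown above.

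| True differences, endpoints 1, 2, 3 | Independent | Correlation 0.5 | Correlation 0.8 |
|---|---|---|---|
| 0, 0, 0 | 7.1–7.3% | 6.4–6.5% | 5.0–5.2% |
| 0, 0, +10 | 4.9% | 4.6–4.7% | 4.0–4.1% |
| +3, 0, +10 | about 2.5% | about 2.5% | about 2.5% |

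No single claim exceeds 2.6% in any setting.

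**Step 5: the proposed sequence.** The six-step order given under the fix has a simulated family error of at most 2.58% over the settings tried, which is 2.5% within simulation error.

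**The case against.** The best case for the plan has four parts.

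- **The family is inferred.** Section 9.1.1.2 ties significance on all three endpoints to non-inferiority, and that chain does hold 2.5%. No sentence states 2.5% for the non-inferiority and superiority tests taken together. This is fair as to wording. But the superiority tests are declared penalty-free in the section on error control, have reach thresholds in Table 4, and are not labelled exploratory, so a reader will take them as controlled.
- **Seven percent is an extreme.** It needs three nulls at their boundary and independent endpoints. Section 3.0 expects outcomes similar to the Q90, and the Synopsis seeks a gain over Omnidirectional. The relevant figure is then 4 to 5%, and there is no inflation if the M90 is also truly better in quiet. This stands as a limit on size; 4 to 5% is still nearly twice 2.5%.
- **A narrower reading exists.** The sentence in 9.1.1.2 says only that non-inferiority testing goes on after a failed superiority test. If superiority were itself ordered across endpoints, three true zeros would give 2.5%. But true differences of 0, -10, 0 would still give about 4.9%, since superiority on endpoint 1 and non-inferiority on endpoint 2 would run side by side. Control at 2.5% fails on either reading, and 9.1.1.1 favours the wider one.
- **Superiority over the Q90 is not an objective.** The Synopsis says no worse. This limits the harm and makes the descriptive option attractive.

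Section 9.1.1.1 also still gives one-sided 0.05 for the primary test. The statement that the non-inferiority chain holds 2.5% rests on the 0.025 in 9.1.1.2 and 9.1.2; at 0.05 that chain would run at 5%.

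**Conclusion.** The concern holds. The hierarchy as written controls the non-inferiority chain and each claim taken singly at about 2.5%, but not the full set of claims that the plan allows. Per cohort, the chance of at least one false claim is at most about 7.3% with independent endpoints, about 5% with all correlations at 0.8, and 4 to 5% under the plan's own expectations. Over both cohorts the ceiling is about 14%.

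The sizes rest on assumed correlations, an assumed SD for endpoint 3, and the reading that each superiority test runs at full alpha once its own non-inferiority test succeeds. The excess comes from the superiority tests, and the primary non-inferiority conclusion is not weakened. This should be fixed before analysis.

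**What to change.** In 9.1.1.1 and 9.1.1.2, remove the penalty-free statements and set one fixed sequence per cohort at one-sided 0.025, stopping at the first failure:

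1. Non-inferiority, endpoint 1
2. Non-inferiority, endpoint 2
3. Non-inferiority, endpoint 3
4. Superiority, endpoint 3, which serves the Synopsis objective "To demonstrate increased speech recognition in noise with the M90 sound processor when comparing" Omnidirectional with AutoSense
5. Superiority, endpoint 1
6. Superiority, endpoint 2

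A simpler alternative keeps steps 1 to 4 and labels superiority over the Q90 as descriptive. Placing each superiority test directly after its own non-inferiority test would also control the error, but a failed superiority test on endpoint 1 would then block non-inferiority on endpoint 2.

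In the same edit, strike the one-sided 0.05 in 9.1.1.1, and add to 9.1.2 and Table 4 that the superiority thresholds count as formal claims only when the earlier steps have succeeded (or are descriptive under the alternative).

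The cost is wording in these sections, with no added subjects or procedures. No non-inferiority claim is lost, nor is the superiority claim on endpoint 3. The price is that formal superiority over the Q90 must wait for steps 1 to 4, with no power given in Table 4 for endpoint 3, or is given up under the alternative.
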